All subjects who are randomized to Caplyta will receive 42mg/day starting the first week of the study. Subjects will be seen every two weeks for 8 weeks. Dosage changes and reductions will not be permitted. After study conclusion (week 8), the dose will be discontinued.

Randomization

Participants are randomized (1:1) to receive placebo or Caplyta by the investigational pharmacy at the University of Chicago. The study blind will be maintained by making placebo and active treatments appear identical in size, weight, shape, and color. Dosage changes and reductions will not be permitted during the study and participants will be discontinued if they experienced intolerance.

Blinding

Blinding is critical to the integrity of this clinical study. However, in the event of a medical emergency or pregnancy in an individual subject, in which knowledge of the investigational product is critical to the subject's management, the blind for that participant may be broken by the treating physician.

Treatment Duration, Visit Frequency, and Procedures

This is an 8-week study (8 weeks of acute treatment). Subjects will be seen at baseline and then every two weeks after that for a total of 5 visits.

Diagnostic Evaluation

Psychiatric evaluation will use the MINI International Neuropsychiatric Interview with a module for BPD.

Assessments at Each Visit

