If a subject withdraws from the study, all instruments administered at the screening visit will be completed at the final visit. These will be conducted when the subject is able to come in for an early termination visit. Withdrawn subjects will be given the phone number of the principal investigator as well as the phone numbers of local resources for BPD treatment.

Subject Termination

If a subject fails to take the medication for a consecutive three-day period, they will be terminated from the study. In this case, the procedures for Subject Withdrawal will be followed (see above). Medication compliance will be assessed via pill count and subject report.

Safety Assessments

Safety and tolerability will be assessed using spontaneously reported adverse events data, C-SSRS, vital signs, and by evaluating premature termination. Safety assessments (sitting blood pressure, heart rate, adverse effects, concomitant medications, and motor tolerability using the Abnormal Involuntary Movement Scale) will be documented at each visit. Subjects who are an immediate suicide risk will be removed from the study and appropriate clinical intervention (e.g. hospitalization) will be arranged. Study team members are mandated reporters and as such, will arrange for the subject to be taken to the emergency room if any intent to harm themselves is expressed. Urine pregnancy tests will be performed at the initial visit. Subjects who have a positive urine pregnancy test will be excluded from the study. Assessment of side effects will be done at each visit.

Adverse Event Reporting

Unanticipated (unexpected) problems/events, those that are *not* already described as potential risks in the consent form, or *not* part of an underlying disease, will be reported to the IRB as soon as possible. The same will be done for serious problems/events and, in the opinion of the investigator, are possibly, probably or definitely related to the research procedures. A follow-up report will also be submitted to the IRB with any documentation related to a previously submitted adverse event.

Risks

While taking the study drug, the subjects condition may remain the same or worsen due to no effect of the study drug.

The most commonly reported side effects (greater than 2%) in previous clinical trials associated with Caplyta include:

24% of subjects experience:

- Somnolence/Sedation (Sleepiness)

14% of subjects experience:

- Headache

6-10% of subjects experience:

- Nausea
- Dry Mouth

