Data collected will consist of demographic data, subjective (self-report questionnaires, interview responses, ratings), physiological (heart rate and blood pressure), and cognitive (e.g., neurocognitive tasks). Access to individually identifiable private information about human subjects will be limited to Drs. [name] and [name] and their staff and will be collected specifically for the proposed research project. All collected data will be stored utilizing a 4-digit subject identification code, linked to separately stored identifying information via a coded log only available to the PIs.

Prior to inferential analyses, descriptive statistics, including distributions, means, standard deviations, skewness, and kurtosis will be generated. Data will also be examined for the pattern and mechanism of missing data. Continuous data will be tested for normality and homogeneity of variance. The integrity of the randomization will be evaluated using t-tests for continuous variables and chi-square tests for categorical variables. Further, baseline differences between those who enter the study and those who drop out before treatment will be evaluated. Subsequent outcome analyses will be adjusted for baseline differences using covariance procedures.

All enrolled subjects will be included in the analyses of baseline demographics and safety according to an intent-to-treat (ITT) principle. For statistical analysis, the full-analysis set will be defined as all participants who took at least 1 dose of the study drug and had at least 1 post-baseline primary efficacy assessment. The safety-analysis set will be defined as all randomized participants who took at least 1 dose of the study drug and completed at least 1 follow-up safety assessment.

The statistical model will be a linear mixed-effects regression model (LME) that includes terms for treatment group, time, and treatment-by-time interaction. The analyses will run using the nlme package on R for Windows (R Foundation, Vienna, Austria; <http://www.r-project.org>). Literature suggests LME without imputation may provide more accurate and stable results than LME models using fixed and multiple imputation methods for handling missing data, so no imputation will be undertaken for missing data. All tests of hypotheses will be performed using a two-sided significance level of 0.05.

Sample Size

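### The plan defines two incompatible safety populations, and the narrower one can exclude a dosed participant who leaves before week 2 and does not return

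*Combined protocol and SAP*

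**What the plan says.** All three population statements stand in consecutive sentences of the Data Analysis section of the combined protocol and SAP.

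- Broad statement: "All enrolled subjects will be included in the analyses of baseline demographics and safety according to an intent-to-treat (ITT) principle".
- Full-analysis set, for efficacy: "all participants who took at least 1 dose of the study drug and had at least 1 post-baseline primary efficacy assessment".
- Safety-analysis set: "all randomized participants who took at least 1 dose of the study drug and completed at least 1 follow-up safety assessment".

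The same section foresees losses before dosing: "baseline differences between those who enter the study and those who drop out before treatment will be evaluated".

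Other sections bear on who would have a follow-up assessment:

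- Treatment Duration, Visit Frequency, and Procedures: "Subjects will be seen at baseline and then every two weeks after that for a total of 5 visits". The first scheduled follow-up is therefore week 2.
- Randomization: "Dosage changes and reductions will not be permitted during the study and participants will be discontinued if they experienced intolerance".
- Subject Withdrawal provides for a final set of assessments after withdrawal, with this condition: "These will be conducted when the subject is able to come in for an early termination visit".
- Safety Assessments names spontaneous adverse event reports, the C-SSRS, vital signs and premature termination as the safety measures.

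**The concern.** A safety analysis needs one denominator, fixed in advance. Here there are two, and no text ranks them or explains how they relate. The choice could be made after the data are seen.

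Each definition also has a fault of its own. The broad one counts people who never took study drug. The narrow one makes membership depend on something that happens after dosing, namely completing a follow-up assessment. Someone who takes drug, stops within two weeks and does not come back has been exposed but can fall outside the set. That person's premature termination, and any event reported by telephone, would then be missing from the tables, although the plan lists both kinds of information as safety data.

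Safety is named alongside efficacy in the primary objective, and with 30 participants per arm a single omission is visible in a percentage.

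**Working it through.** **Step 1. Compare the two definitions.** The plan states no figure for this point, so the first check is a comparison of texts.

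| Participant | Broad statement | Safety-analysis set |
|---|---|---|
| Enrolled, never dosed | in | out |
| Dosed, left before week 2, no early termination visit | in | out, if an assessment means a visit |
| Dosed, left before week 2, attended early termination visit | in | probably in |
| Dosed, seen at week 2 or later | in | in |

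The first row alone makes the definitions incompatible, and it needs no assumption: the plan itself expects some people to drop out before treatment.

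**Step 2. Routes into the second row.** Three provisions can end participation before week 2: discontinuation for intolerance (Randomization), termination after three consecutive days without medication (Subject Termination), and removal for immediate suicide risk (Safety Assessments). The early termination visit then depends on the person being able to attend.

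**Step 3. Effect on a rate when the event is known.** Inputs: n = 30 dosed per arm (60 randomized 1:1, all assumed dosed); e = dosed participants with a known event but no follow-up assessment; a = participants with the event among the rest. Both e and a are assumptions.

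- All dosed: (a + e)/n
- Stated safety set: a/(n − e)

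| a | e | All dosed | Stated set | Difference (points) |
|---|---|---|---|---|
| 3 | 1 | 4/30 = 13.3% | 3/29 = 10.3% | 3.0 |
| 3 | 2 | 5/30 = 16.7% | 3/28 = 10.7% | 6.0 |
| 3 | 3 | 6/30 = 20.0% | 3/27 = 11.1% | 8.9 |
| 0 | 1 | 1/30 = 3.3% | 0/29 = 0% | 3.3 |
| 0 | 3 | 3/30 = 10.0% | 0/27 = 0% | 10.0 |

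Each excluded participant with a known event therefore moves the rate by about 3 percentage points. The same formulas apply to premature termination if it is tabulated in this set. A departure is known without a visit, so there the condition of a known event is met for every excluded leaver, whatever the reason for leaving.

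**Step 4. Effect when the lost participant has no known event.** With a = 3 and one such loss, the stated set gives 3/29 = 10.3% and the all-dosed set 3/30 = 10.0%. With three such losses the figures are 3/27 = 11.1% and 3/30 = 10.0%. The direction reverses, because only the denominator shrinks.

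**Step 5. Would it happen at all?** If a proportion q of dosed participants left with no follow-up assessment, the chance of at least one among 60 is 1 − (1 − q)^60. For q = 2%, 5% and 10% this is 70%, 95% and 99.8%. These values of q are assumed; the Sample Size section expects few drop-outs and gives no rate.

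**The case against.** **The early termination visit.** Subject Withdrawal provides that withdrawn participants repeat the instruments given at screening. The baseline list includes the C-SSRS, itself a safety measure, so an early leaver who attends probably stays in the set. This stands. A reader might infer that the definition removes everyone who leaves early with an adverse event; the documents do not support that. The exposed group is those who leave before week 2 and never return.

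**An undefined term.** The plan does not say what a follow-up safety assessment is. Since spontaneous reports are listed as a way of assessing safety, a telephoned event might qualify. This also stands, and it is why exclusion is possible rather than certain. It does not remove the problem, because a known event may be in or out depending on a reading the plan does not settle.

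**General principle and operational definition.** The broad sentence could be taken as a principle and the later one as the working definition. The plan does not say so, and on that reading the follow-up condition still applies.

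**Size.** It is tempting to apply the 24% sedation rate in the Risks section. About 7 of 30 (0.24 × 30 = 7.2) would be affected, 23%, and if three of them were lost the stated set would show 4/27, 15%. That contrast holds only if the three events were reported without a visit. If they were not, the all-dosed set gives 4/30, 13%, which is lower still. The 24% is also an occurrence rate from previous trials, and nothing links it to early departure.

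**Direction.** A reader might infer that losses fall mainly on Caplyta and that event rates are biased downward. Both are plausible if intolerance is drug-related, but the documents show neither. Step 4 shows that losses without a known event push the rate up.

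**Serious events.** A reader might infer that a serious early event could go unseen. The Data and Safety Monitoring Plan requires written reporting of any serious adverse event to the IRB, and the PI prepares written adverse event summaries. The gap is in the analysed and reported rates, not in oversight.

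**Conclusion.** The safety populations are wrong as written. They are incompatible, no text says which governs, and this conclusion needs no assumption. The narrower one can also exclude a dosed participant who leaves before week 2 and does not attend the early termination visit, although that departure and any spontaneous report are safety data under the plan.

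If these losses are related to tolerability, adverse event and discontinuation rates would be understated, by about 3 percentage points per excluded participant with a known event at 30 per arm. This size rests on an assumed number lost and, for event rates, on the event having been reported without a visit. A concentration of losses on Caplyta and a certain downward bias are not established.

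**What to change.** In the Data Analysis section, define a single safety set: every randomized participant who received one or more doses, with no condition on follow-up. State that adverse events and discontinuations count whatever the route of report, including telephone. Confine the enrolled-subjects sentence to baseline demographics and disposition.

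Report for each arm how many participants in the safety set have no post-dose data. They stay in the denominator and, as Step 4 shows, can dilute a rate if their events are unknown.

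The cost is a small change of wording made before unblinding. It needs no extra visits, participants or data collection and alters no clinical rule. Reported rates may be slightly less favourable.
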